3.4.1. Treatment scheme and DLT observation period

- Olaparib will be given orally, continuously, twice a day, as appropriate for assigned dose level, from D1 to the end of radiotherapy. Olaparib will be started one week before the start of radiotherapy and will be continued until the last day of radiotherapy. Beyond this period, Olaparib could be continued until progression, at the investigator's discretion and sponsor approval.
- Radiotherapy consists of fractionated focal irradiation at a dose of 1.8 Grays (Gy) per fraction given once daily five days per week (Monday through Friday), for a total dose of 59.4 Gy (i.e 33 fractions). Radiotherapy starts at D8.
- The DLT observation period is defined as the first day of Olaparib intake and up to 6 weeks after the end of radiotherapy (13.5 weeks).

3.4.2. Dose levels

- Dose escalation study assessing 4 dose levels of Olaparib in association with concomitant radiotherapy.

Level	-1	1	2	3	4
Olaparib	25 mg (daily)	25 mg (b.i.d)	50 mg (b.i.d)	100 mg (b.i.d)	150 mg (b.i.d)

- The starting dose of Olaparib is 25 mg b.i.d.
- The maximum dose of Olaparib administered (150 mg x 2) will not be exceeded.
- No skipping of the dose will be allowed.
- For a given patient, dose will never be escalated.
- **As long as no DLT is observed**, patients will be allocated to 4 dose levels following a 3+3 design with the following characteristics:
 - Inclusions of cohorts of 3 patients,
 - At dose levels 1 and 2, before accrual to next higher dose level, at least 2 patients with 6-week follow-up will be required,
 - At dose level 3, before accrual to dose level 4, at least 2 patients with 8-week follow-up will be required

- **As soon as the first DLT is observed**, patients will be allocated following a TITE-CRM design [Normolle et al. Statistics in Medicine 2003]. When a patient is eligible for enrollment, the probability of DLT is estimated for each dose level, based on the trial experience up to that time and the prior expectations for toxicity.
 - Each new patient is assigned to the currently estimated target dose, defined as the dose having an estimated probability of toxicity closest to but not greater than the target rate (33%), subject to the following restrictions :
 - A minimum of 2 patients will be entered on each dose level,
 - At dose levels 1 and 2, before accrual to next higher dose level, at least 2 patients with 6-week follow-up will be required,
 - At dose level 3, before accrual to next higher dose level, at least 2 patients with 8-week follow-up will be required,
 - In case of important accrual rate, to maintain operating characteristics of TITE-CRM design and patient safety, the Sponsors might decide to suspend the inclusions.
 - The prior distribution of the dose-toxicity model will be chosen to control the expected number of toxicities in the trial under a variety of scenarios about the true relationship between dose and toxicity.
 - In the TITE-CRM paradigm, patients who have been enrolled in the trial but have not experienced DLT are included in the probability calculation with a weight equal to the proportion of the 13.5-week DLT observation period they have completed; patients who experience toxicity or completed the observation period without toxicity are assigned full weight.
 - Stopping rule: inclusions will stop in the dose escalation trial after 24 eligible and assessable patients enrolled.
- For the dose escalation part, a DLT validation committee will be consulted before the first escalation to a new dose level (see section 12.1.2).
- Conclusions of the steering committee for the MTD definition will be submitted to an independent committee (IDMC) before opening the expansion cohort.

3.5.EXPANSION COHORT

- Once the MTD and the RP2D have been defined based on the dose escalation study, the expansion cohort will be opened. All patients will be treated at the RP2D of Olaparib (as defined in the escalation trial) given in association with concomitant radiotherapy at a dose that depends on tumor status:
 - Resectable tumor or potentially resectable tumor after study treatment: up to 50 Gy
 - Unresectable tumor: up to 59.4 Gy.
- Following the expansion cohort, the **RP2D for Olaparib** may be refined by the steering committee based on the MTD and RP2D (as defined at the end of the dose escalation trial), as well as additional safety data including safety data from the expansion cohort, PK and PD data. Data from all patients (escalation + expansion) will be used to refine the RP2D.

3.6.PATIENT'S REPLACEMENT

See section 10.2

4. SELECTION OF PATIENTS

4.1. INCLUSION CRITERIA

1. Histology: patients with soft-tissue sarcoma histologically confirmed by central review (Pr [name] team), except if the diagnosis was already confirmed by the RRePS Network,
2. Upper/Lower limb or trunk wall soft-tissue sarcoma,
3. Age ≥ 18 years,
4. Locally advanced or locally recurrent primitive tumor, outside any previously irradiated field. Patients presenting operable locally advanced or locally recurrent tumor can be included. Patients with metastases can be included in the protocol,
5. Eastern Cooperative Oncology Group (ECOG), performance status ≤ 2 ,
6. Life expectancy ≥ 6 months,
7. At least one lesion, not previously irradiated, that can be accurately measured at baseline as ≥ 10 mm in the longest diameter (except lymph nodes which must have short axis ≥ 15 mm) with magnetic resonance imaging (MRI) and which is suitable for accurate repeated measurements,
8. Adequate hematological, renal, metabolic and hepatic function:
 - Haemoglobin ≥ 9 g/dL and no blood transfusions in the 14 days prior to study entry
 - Absolute neutrophil count (ANC) $\geq 1.5 \times 10^9/L$
 - Platelets $\geq 100 \times 10^9/L$
 - Total bilirubin $\leq 1.5 \times$ upper limit of normality (ULN),
 - Alanine aminotransferase (ALAT) or aspartate aminotransferase (ASAT) $\leq 2.5 \times$ ULN,
 - Serum creatinine $\leq 150 \mu\text{mol/L}$ or creatinine clearance $\geq 50 \text{ mL/min}$ (according to local institution) in case of serum creatinine $> 150 \mu\text{mol/L}$,
 - TP, INR $\leq 1.5 \times$ ULN
9. Women of childbearing potential must have a negative serum pregnancy test within 28 days of study treatment, confirmed prior to treatment on day 1. Female patients of child bearing potential and their partners, who are sexually active, must agree to the use of two highly effective forms of contraception in combination throughout the period of taking study treatment and for at least 1 month after last dose of study drug. Males patients, who are sexually active, and their partners of child bearing potential must agree to the use of two highly effective forms of contraception in combination throughout the period of taking study treatment and for at least 3 month after last dose of study drug. Acceptable birth control methods are described in appendix 6. Subjects of non-childbearing potential are those who have:
 - Amenorrheic for 1 year or more following cessation of exogenous hormonal treatments,
 - LH and FSH levels in the post menopausal range for women under 50,
 - radiation-induced oophorectomy with last menses > 1 year ago,
 - chemotherapy-induced menopause with > 1 year interval since last menses,
 - or surgical sterilisation (bilateral oophorectomy or hysterectomy).
10. Patient is willing and able to comply with the protocol for the duration of the study including undergoing treatment and scheduled visits and examinations including follow up,
11. Voluntary signed and dated written informed consent prior to any specific procedure,
12. Patients with a social security in compliance with the law.

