4.2. NON-INCLUSION CRITERIA

1. Any previous treatment with a PARP inhibitor, including Olaparib,
2. Patients unable to swallow orally administered medication and patients with gastrointestinal disorders likely to interfere with absorption of the study medication,
3. Immunocompromised patients, e.g., patients who are known to be serologically positive for human immunodeficiency virus (HIV) and are receiving antiviral therapy,
4. Patients with known active hepatic disease (i.e., Hepatitis B or C) due to risk of transmitting the infection through blood or other body fluids,
5. Patients considered a poor medical risk due to a serious, uncontrolled medical disorder, non-malignant systemic disease or active, uncontrolled infection. Examples include, but are not limited to, uncontrolled ventricular arrhythmia, recent (within 3 months) myocardial infarction, unstable spinal cord compression (untreated and unstable for at least 28 days prior to study entry), superior vena cava syndrome, extensive bilateral lung disease on HRCT scan or any psychiatric disorder that prohibits obtaining informed consent,
6. Patients with uncontrolled seizures,
7. Men or women of childbearing potential who are not using an effective method of contraception as previously describes; women who are pregnant or breast feeding,

8. Prior or concurrent malignant disease diagnosed or treated in the last 2 years, except for adequately treated in situ carcinoma of the cervix, basal or squamous skin cell carcinoma, or in situ transitional bladder cell carcinoma,
9. Patients receiving any systemic chemotherapy, radiotherapy (except for palliative reasons), within 2 weeks from the last dose prior to study treatment (or a longer period depending on the defined characteristics of the agents used),
10. Concomitant use of known strong CYP3A4 inhibitors (such as ketoconazole, itraconazole, boosted protease inhibitors, indinavir, saquinavir, telithromycin, clarithromycin, nelfinavir, boceprevir and telaprevir), moderate CYP3A4 inhibitors (such as ciprofloxacin, erythromycin, diltiazem, fluconazole, verapamil), strong CYP3A4 inducers (such as phenobarbital, enzalutamide, phenytoin, rifampicin, rifabutin, rifapentine, carbamazepine, nevirapine and St John's Wort) and moderate CYP3A4 inducers (such as bosentan, efavirenz, modafinil),
11. Resting ECG with QTc > 470msec on 2 or more time points within a 24 hour period or family history of long QT syndrome,

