11.2.2. Serious adverse event

A serious adverse event is an AE occurring during any study phase (i.e., screening, run-in, treatment, wash-out, follow-up), at any dose of the study drugs that fulfils one or more of the following criteria:

- Results in death
- Is immediately life-threatening
- Requires in-patient hospitalization or prolongation of existing hospitalization
- Results in persistent or significant disability or incapacity
- Is a congenital abnormality or birth defect
- Is an important medical event that may jeopardize the patient or may require medical intervention to prevent one of the outcomes listed above.

The causality of SAEs (their relationship to all study treatment/procedures) will be assessed by the investigator(s) and communicated to Sponsor.

Any suspected transmission via a medicinal product of an infectious agent, pathogenic or non-pathogenic, is assessed as a serious adverse event with the seriousness criterion important medical event. The event may be suspected from clinical symptoms or laboratory findings indicating an infection in a patient exposed to a medicinal product. The terms "suspected transmission" and "transmission" are considered synonymous.

Any abnormal laboratory's result resulting as a grade 4 in the CTCAE version 4 will be considered as serious adverse event even if this event is not clinically relevant.

Whether or not corresponding to the above-mentioned criteria, any other adverse event considered as serious by any IMP, any healthcare professional or any investigator should be handled as a serious adverse event.

NB. Cases where a subject shows an AST or ALT $\geq 3 \times \text{ULN}$ or total bilirubin $\geq 2 \times \text{ULN}$ may need to be reported as SAEs.

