12.2.2. Monitoring

In order to guarantee the authenticity and credibility of the data in accordance with the principles of GCP (Good Clinical Practice) dated 24 November 2006, the sponsor shall implement a quality assurance system comprising:

- the management and monitoring of the trial in accordance with the procedures stipulated by the Institut Bergonié,
- the quality control of the research site data by the CRA whose role is to:
 - check compliance with the protocol, GCP and current legislation and regulations,
 - check the consent and eligibility of each patient taking part in the trial,
 - check the consistency and coherence of case report form data against the source documents.
 - check that each serious adverse event is reported,
 - monitor the traceability of the study medication (dispensation, storage and drug accountability),
 - check, where applicable, that the persons likely to take part in the trial are not already participating in another trial that could prevent them from being included in the clinical

trial proposed. The CRA shall also ensure that the patients have not participated in a trial for which an exclusion period currently applies.

- The possible audit of study centers
- The centralized review of certain protocol criteria.

The check procedures will include:

- Study progression,
- Protocol compliance,
- The updating of information on the Internet site.

The checking of data by comparing the information on the electronic case report form and the original clinical or laboratory data is one of the monitoring procedures.

The following will be checked, in particular, for each patient (100% level): patient identification, informed consent (procedure and signature), selection criteria, therapeutic procedure, adverse events, principal response variables. The personal data relating to each patient shall remain confidential. On the electronic case report form or any other form dispatched, the patients will be identified solely by their initials (1/name – 1/surname) and an inclusion number. However, the investigators must keep a list identifying the patients in their folders.

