
function:
 
 
- Haemoglobin <math>\geq 9</math> g/dL and no blood transfusions in the 14 days prior to study entry
 
- Absolute neutrophil count (ANC) <math>\geq 1.5 \times 10^9/L</math>
 
- Platelets <math>\geq 100 \times 10^9/L</math>
 
- Total bilirubin <math>\leq 1.5 \times</math> upper limit of normality (ULN),
 
- Alanine aminotransferase (ALAT) or aspartate aminotransferase (ASAT) <math>\leq 2.5 \times</math> ULN,
 
- Serum creatinine <math>\leq 150 \mu\text{mol/L}</math> or creatinine clearance <math>\geq 50 \text{ mL/min}</math> (according to local institution) in case of serum creatinine <math>> 150 \mu\text{mol/L}</math>,
 
- TP, INR <math>\leq 1.5 \times</math> ULN
 
	
HEMO NEUT PLAT BIL_TOT ALT AST CREA CCLE TP INR
	
PLAT <math>\geq 100 \times 10^9</math> CREA <math>\leq 150</math> or CCLE <math>\geq 50</math>

9. Women of childbearing potential must have a negative serum pregnancy test within 28 days of study treatment, confirmed prior to treatment on day 1. Female patients of child bearing potential and their partners, who are sexually active, must agree to the use of two highly effective forms of contraception in combination throughout the period of taking study treatment and for at least 1 month after last dose of study drug. Males patients, who are sexually active, must agree to the use of two highly effective forms of contraception in combination throughout the period of taking study treatment and for at least 3 month after last dose of study drug. Acceptable birth control methods are described in appendix 10. Subjects of non-childbearing
	
ELIGFORM C9I INCFORM FEM_STA DT_PREG RES_PREG FEM_REA (non childbearing potential) REA_OTH TRT_OLA DT_S10 (D1 olaparib) PRE3TRT CONT_PTR (contraception) SPE_CONT
	
C9I=1
 
(FEM_STA =1 and RES_PREG=0 and (DT_S10-DT_PREG <math>\leq 28</math>))
 
(CONT_PTR =1 and check SPE_CONT)
 
If (FEM_STA =0 ) then Check FEM_REA and REA_OTH

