18. Patients with a known hypersensitivity to olaparib or any of the excipients of the product.	ELIGFORM C18NI	C18NI=0 Investigator decision

Criteria	eFORM variable	Control
Eligible Population	ELIGIBILITY FORM C1I C2I C3I C4I C5I C6I C7I C8I C9I C10I C11I C12I C1NI C2NI C3NI C4NI C5NI C6NI C7NI C8NI C9NI C10NI C11NI C12NI C13NI C14NI C15NI C16NI C17NI C18NI	ELI=1 If (C1I=0 OR C2I=0 OR C3I=0 OR C4I=0 OR C5I=0 OR C6I=0 OR C7I=0 OR C8I=0 OR C9I=0 OR C10I=0 OR C11I=0 OR C12I=0 OR C1NI=1 OR C2NI=1 OR C3NI=1 OR C4NI=1 OR C5NI=1 OR C6NI=1 OR C7NI=1 OR C8NI=1 OR C9NI=1 OR C10NI=1 OR C11NI=1 OR C12NI=1 OR C13NI=1 OR C14NI=1 OR C15NI OR C16NI=1 OR C17NI=1 OR C18NI=1) then ELI=0

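### Inclusion criterion 8 joins ALAT and ASAT with 'or', so as written one enzyme within 2.5 x ULN is enough and the other has no ceiling at entry

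*Protocol*

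**What the plan says.** Protocol 4.1, inclusion criterion 8, requires adequate hematological, renal, metabolic and hepatic function and lists seven laboratory bullets. The transaminase bullet begins "Alanine aminotransferase (ALAT) or aspartate aminotransferase (ASAT" and sets one limit for the pair, 2.5 x ULN. The same wording appears in the protocol synopsis, the SAP synopsis (1.1) and the criteria column of SAP 2.2.1. I found no statement in either document that both enzymes must be within the limit.

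The next bullet, on renal function, also uses 'or'. It accepts a serum creatinine up to 150 µmol/L "or creatinine clearance" of at least 50 mL/min when creatinine is above that value.

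SAP 2.2.1 lists ALT and AST among the variables for criterion 8. Its control column requires the tick-box C8I=1 and sets numeric conditions for haemoglobin, neutrophils, platelets and renal function, the last as "CREA \leq 150 or CCLE \geq 50". It sets none for ALT or AST. The eligibility flag ELI, defined at the end of SAP 2.2.2, is set to 0 from tick-box answers alone ("C7I=0 OR C8I=0 OR C9I=0" is part of the rule).

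**The concern.** An entry limit on liver enzymes should have one meaning at every site. As worded, a candidate with one enzyme within 2.5 x ULN meets the bullet whatever the value of the other, so the plan sets no upper bound on the second enzyme at entry.

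What is at stake is who may enter on a safety criterion in a trial that combines olaparib with radiotherapy. Two sites could also reach different decisions on the same laboratory report and both be following the text.

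**Working it through.** No sample size, power or event count bears on this point, and the plan states no figure to reproduce. The check is a comparison of texts and a truth table.

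**Step 1: what the rule admits.** The limit is 2.5 x ULN (Protocol 4.1).

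| ALAT | ASAT | Met under 'or' | Met under 'and' |
|---|---|---|---|
| ≤ 2.5 x ULN | ≤ 2.5 x ULN | yes | yes |
| ≤ 2.5 x ULN | > 2.5 x ULN | yes | no |
| > 2.5 x ULN | ≤ 2.5 x ULN | yes | no |
| > 2.5 x ULN | > 2.5 x ULN | no | no |

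The literal 'or' admits 3 of 4 combinations and 'and' admits 1 of 4. With assumed values for illustration, ALAT 1 x ULN and ASAT 4 x ULN passes under 'or' and fails under 'and'. The cells are not equally likely, so 3 against 1 describes the rule and not a patient count.

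**Step 2: does anything else cap the second enzyme?**
- Bilirubin and TP/INR are separate bullets of criterion 8. They limit other markers of liver function.
- Non-inclusion criterion 4 excludes "Patients with known active hepatic disease (i.e., Hepatitis B or C"). It sets no enzyme level.
- Non-inclusion criterion 5 excludes patients at poor medical risk from serious uncontrolled disease. It sets no enzyme level.
- Protocol 5.5 repeats biochemistry up to 48 hours before Day 1 and on Days 15, 29 and 43. The pre-treatment repeat brings no enzyme threshold of its own, and the later tests come after entry.
- Protocol 7.1.6.9 covers hepatic impairment that develops on treatment.

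Each reduces the risk; none bounds the second enzyme at entry.

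**Step 3: would data checks catch it?** SAP 2.2.1 lists ten laboratory variables for criterion 8: HEMO, NEUT, PLAT, BIL_TOT, ALT, AST, CREA, CCLE, TP and INR. Five have a numeric condition (HEMO, NEUT, PLAT, CREA, CCLE) and 10 − 5 = 5 have none (BIL_TOT, ALT, AST, TP, INR). The five without one are the limits expressed as multiples of ULN. C8I covers the enzymes indirectly, but it records the investigator's own reading of the bullet. Under Protocol 12.2.2 the CRA will "check the consent and eligibility of each patient taking part in the trial", and the items checked for every patient include "selection criteria, therapeutic procedure, adverse events, principal response variables". That review applies the same wording, so a patient admitted on the literal 'or' passes it.

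**The case against.** The strongest reply is that the intent is clear enough. The heading of criterion 8 asks for adequate hepatic function, and the transaminase bullet gives one threshold for both enzymes. Where the authors mean a true alternative, as with creatinine, they give two thresholds and say when the second applies. On that view a sensible investigator reads the bullet as both enzymes, and C8I plus full monitoring of selection criteria is control enough. Much of this stands: the intent probably is 'both', and the creatinine bullet can be argued either way. It does not settle the point, because the text as written still passes a patient with one uncapped enzyme, and every later check relies on that text.

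A reader might infer more than the documents support:
- *That patients could enter with a reportable serious event already present.* Protocol 11.2.2 and 11.8.2 carry a note that begins "Cases where a subject shows an AST or ALT" and refers to values of at least 3 x ULN. The note says only that such cases may need reporting. Protocol 11.2.1 defines an adverse event as a condition that develops or deteriorates, and 11.8.2 speaks of deterioration from baseline. A stable raised value at entry is not by itself an adverse event, so the gap between 2.5 and 3 x ULN shows no harm.
- *That DLT counts would be inflated.* The laboratory DLT criterion in Protocol 3.3 exempts enzyme changes without clinical impact. No effect on DLT counts is shown.
- *That the missing SAP conditions distort the eligible population.* ELI uses tick-boxes only, and a patient admitted on the literal 'or' violates no criterion. Neither ELI nor the primary-endpoint population in Protocol 10.2 is shown to change.

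**Conclusion.** The point holds as a minor patient-safety wording correction. Criterion 8, applied exactly as written in four places, is met with only one transaminase within 2.5 x ULN, and no other provision caps the other at entry. This rests on the literal text; I take the intent to be that both comply.

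Its size in patients cannot be given, because the documents do not say how often exactly one enzyme exceeds the limit. It is probably small. Protocol 7.1.6.2 already tabulates the RP2D as 100 mg b.i.d., which suggests that escalation is complete. If so, a change would reach at most the planned 15 expansion patients and any replacements. No effect on DLT counts, analysis populations, sample size or error rates is shown.

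**What to change.** Write 'ALAT and ASAT ≤ 2.5 x ULN' in the protocol synopsis, Protocol 4.1, the SAP synopsis and the criteria column of SAP 2.2.1. Protocol 13.1 requires ethics committee and ANSM approval for amendments that concern the patient population, so the change is best carried in the next amendment. The SAP can follow under the updating rule in Protocol 10.3. No new test is needed, since ALT, AST and bilirubin are already in the screening panel (Protocol 5.4). The downside is that a few candidates with one raised enzyme become ineligible.

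Optionally, add conditions to the control column of SAP 2.2.1 as a data check on C8I: ALT and AST each at most 2.5 x ULN, and total bilirubin at most 1.5 x ULN, against the local ULN. ELI stays as defined. The cost is recording the local ULN for three analytes at each of the five centres in the protocol synopsis. I would not extend this check to TP: the notes to the table in Protocol 5.4 expand it as a prothrombin rate, for which an upper limit is not a sound test.
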